## Treatment Dosage and Administration

RPS or placebo will be administered at ~20 grams (2 tablespoons) once daily for days 1-3 and then twice daily for days 4-14, (**Table 2**).

Intervention and Placebo:

**Table 2.** Intervention and Placebo

|              |                                    |   |
|--------------|------------------------------------|---|
| Intervention | Study Product, Dose, Route Regimen | Food Source (used as a drug): Potato based dietary starch, Bob's Red Mill®, ~20 grams (2 tablespoons) orally twice daily. (start with 2 tablespoons once daily for 3 days, followed by twice daily on days 4 to 14 to minimize GI symptoms) |
|              | Duration of Administration         | 14 days   |
| Placebo      | Study Product, Dose, Route Regimen | Food Source (used as a drug): Corn based dietary starch by Bob's Red Mill, ~20 grams (2 tablespoons) orally twice daily. (start with 2 tablespoons once daily for 3 days, followed by twice daily on days 4 to 14)                          |
|              | Duration of Administration         | 14 days   |

- Storage and stability: Avoid extremes of temperature. No need for refrigeration.
- Preparation and Dispensing: Mix 2 tablespoons of dietary starch (~20 grams) with any amount water, juice, applesauce or any other cool substance to make palatable. Starch substance should not be heated or warmed.
- Other administration instructions: No regulation for administration of starch with or without other food or medications. As this is a commercially available food product, subjects can keep any remaining product at the end of study. We will determine compliance via questionnaire that will be utilized during phone follow ups (**see attached questionnaire**). Doses should be administered twice daily. Although we suggest the doses be spread apart to minimize any potential GI disturbance, there is no limit as to how closely together doses can be given. For example, doses do NOT need to be given 12 hours apart and instead can be given at times that feel comfortable to the subject.
- Missed doses should be documented by the research team during phone follow up
- Missed doses should simply be skipped with no need to make up this dose at a later time.
- Availability: Commercially Available

## Toxicities and Dosing Delays/Dose Modifications

- This study investigates a food source used as a drug but has been given Discretion Exemption from the FDA. While there are many potential sources for a potato-based or corn-based starch, we have chosen to use starch produced by Bob's Red Mill® because it is easily commercially available, economical and previously well tolerated in our preliminary data.
- Starches are regulated by the Food and Drug Administration (FDA). The FDA's Select Committee on GRAS (Generally Recognized as Safe) Substances published an opinion in 1979 that stated: "There is no evidence in the available information on unmodified or pregelatinized corn, high amylose corn, waxy maize, wheat, milo (also called grain sorghum starch), rice, potato, tapioca or arrowroot starch that demonstrates or suggests reasonable grounds to suspect a hazard to the public when they are used at levels that are now current or that might reasonably be expected in the future" (SCOGS 1979).
- Drug Interactions: None known
- As starch is a natural nutritional supplement used for gluten free baking and cooking, we anticipate none to minimal risk to participants. Some possible side effects to starch are flatulence (gas), abdominal bloating and chalky taste in the mouth. However, the majority of patients do not experience any symptoms when ingesting the dietary supplement. Below are the symptoms that may be experienced from the starch listed as possible, infrequent, and rare:

**Possible 10-25 %:** flatulence (gas), bloating, chalky taste in your mouth after drinking the starch, which resolves quickly

**Infrequent 5-10 %:** abdominal cramps, diarrhea, nausea, vomiting

**Rare <5%:** allergy to starch

Although very minimal adverse events and no serious adverse events were observed in our preliminary data, we have compiled a list of possible adverse events that will need to be reported to the safety monitoring coordinators (**Table 3**).

- Drug Interactions: None known

**Table 3.** Possible adverse events secondary to dietary starch use that will need to be reported to safety monitor

|  |  |  |
|--|--|--|
| Adverse events related to
Resistant Potato Starch (RPS) | 
 
• Allergy to potato or corn based starch
 
• Persistent* Abdominal cramping or pain
 
• Nausea or vomiting
 
• Diarrhea
 
• Persistent Bloating
 
• Persistent Flatulence
 
 | All will be reported within 1 to 5 days to safety monitoring coordinator of event becoming known to PI at each site. |
|--|--|--|

\*Persistent symptoms will be defined as lasting 72 hours or longer

- If persistent side effects related to the investigational agent occur, a dose reduction can be made to once daily instead of twice daily dosing at the discretion of the PI or Co-I. If intolerance continues, despite decreasing the frequency of dosing, the investigational agent may be held for up to 3 days. Investigational agent can also be held for up to 3 days if the patient is unable to take oral intake for any reason. If investigational agent is held longer than 3 days, subject will be removed from treatment and included with an intention to treat protocol.
- The study intervention will be discontinued if patient meets the primary study endpoint of hospitalization

The Placebo uses corn starch. A potential risk although rare is allergy to corn. We will in screening ask about the potential subjects' exposure to corn and any reaction or avoidance of corn. Allergies to corn are extremely rare and there are no recent literature documenting specific rates, but one study from 1950 showed a very low rate of 0.16% (DOI:[https://doi.org/10.1016/0021-8707\(50\)90098-0](https://doi.org/10.1016/0021-8707(50)90098-0)).

**Concomitant Medications/Treatments**

The only concomitant medications prohibited on the study are anti-IL 6 inhibitors such as Tociluzimab which is one of the exclusion criteria. Tociluzimab is usually started as an inpatient so we don't anticipate our patient population will be prescribed this medication while on study, since subjects will only continue to receive the investigational agent (starch) if they are not hospitalized.

**Other Modalities or Procedures:**

Only English-speaking patients will be mailed an instruction sheet with their investigational agent.

**Duration of Therapy**

Treatment will continue for 14 days, or until one of the following criteria apply:

- Hospitalization
- Death
- Persistent adverse event(s) leading to the investigational agent to be held for longer than 3 days
- Subject voluntarily withdraws from treatment **OR**
- General or specific changes in the subject's condition render the subject unacceptable for further treatment in the judgment of the investigator

**Off Treatment Criteria**

Patients will be removed from protocol therapy when any of the criteria listed above. The reason for ending protocol therapy and the date the patient was removed from treatment will be documented. All patients who discontinue treatment should comply with protocol specific follow-up procedures. The only exception to this requirement is when a subject withdraws consent for all study procedures or loses the ability to consent freely.

### **Duration of Follow-Up**

Subjects will be followed for 4 months from positive COVID-19 test or until death, whichever occurs first. Subjects will be followed for adverse events for at least 30 days after the last dose of study drug. Subjects removed from treatment for persistent adverse events thought to be due to interventional treatment will be followed until resolution or stabilization of the adverse event

### **Off Study Criteria**

Patients can be taken off study at any time at their own request, or they may be withdrawn at the discretion of the investigator for safety, behavioral or administrative reasons. The reason(s) for discontinuation from study will be documented and may include:

- Patient withdraws consent (termination of treatment and follow-up);
- Loss of ability to freely provide consent through imprisonment or involuntary incarceration for treatment;
- Patient is unable to comply with protocol requirements;
- Investigators judge continuation on the study would not be in the patients best interest;
- Lost to Follow-up. If a research subject cannot be located to document hospitalization, the subject may be considered “lost to follow-up.” All attempts to contact the subject during the four-month period must be documented.
- Termination of the study by any of the participating IRBs or FDA.
- Patient completes protocol treatment and follow-up criteria.

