We will analyze the efficacy of RPS in relation to the primary outcome of hospitalization. If there is a significant difference between the two arm with p-value of <0.01, we will not continue the study. For data quality and integrity, we will also analyze the efficacy of RPS in relation to the secondary outcomes of TTCA and symptom severity score to assess efficacy and ensure no increase in harm in the intervention arm.

**Section 14. Statistical Considerations:** Describe the statistical analyses that support the study design.

**Study design/Study outcomes measures:** We will conduct a double-blinded, randomized clinical trial comparing RPS (~20g twice daily for 14 days) with placebo (non-resistant starch) in 1500 adults (age  $\geq 18$  years old) with COVID-19 diagnosis (defined by a positive swab) who are being managed in the outpatient setting. The primary outcome is hospital admission due to COVID-19 related complications. The secondary outcomes are TTCA and symptom severity score. We also will investigate some exploratory outcomes such as ER visits without admission, and among those hospitalized, we will explore differences in oxygen requirement, need for mechanical ventilation, duration of ventilation, length of hospital stay, levels of inflammatory markers routinely ordered as part of clinical care (CRP, LDH, D-dimer, Ferritin, IL-6), and rates of discharge between the RPS and placebo arms.

**Sample size and accrual:** Assuming a 14% admission rate in the placebo group, we calculated that a sample size of 1362 (we will enroll 1500 to account for 10% loss to follow up) will be required to provide 80% power (with a two-sided alpha level of 0.04 to detect an absolute reduction in hospital admission rates of 5% or more in the RPS group. **The primary analysis will be based on the intention-to-treat principle, with all patients included in their assigned group.**

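### Off Study Criteria allows removal from the study for reasons that Off Treatment Criteria does not exempt from follow-up, and no rule covers the primary outcomes that may then be missing

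*Combined protocol and SAP*

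**What the plan says.** Under Off Treatment Criteria, "All patients who discontinue treatment should comply with protocol specific follow-up procedures". The next sentence limits this: "The only exception to this requirement is when a subject withdraws consent for all study procedures or loses the ability to consent freely".

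Off Study Criteria is a separate heading with a longer list. Participants may leave at their own request, or "they may be withdrawn at the discretion of the investigator for safety, behavioral or administrative reasons". The listed reasons include "Patient is unable to comply with protocol requirements" and "Investigators judge continuation on the study would not be in the patients best interest". The consent item alone spells out its consequence: "Patient withdraws consent (termination of treatment and follow-up". Loss of free consent is tied there to imprisonment or involuntary incarceration, a limit that Off Treatment Criteria does not state. Loss to follow-up is also listed, in permissive wording.

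Other sections point towards retention. Toxicities and Dosing Delays/Dose Modifications says: "If investigational agent is held longer than 3 days, subject will be removed from treatment and included with an intention to treat protocol". Duration of Follow-Up gives four months from the positive test, or death. Subject Replacement bars replacing anyone who goes off study after randomization, citing intention to treat. Section 14 states: "The primary analysis will be based on the intention-to-treat principle, with all patients included in their assigned group".

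Hospitalization is assessed by phone and EHR (Procedures during treatment and follow up procedures), and Table 4 schedules EHR review to day 120.

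**The concern.** The two sections give different answers for the same person. Someone who stops the product and is judged unable to comply, or is withdrawn on the investigator's judgement, stays in follow-up under Off Treatment Criteria but may be taken off the study under Off Study Criteria. Nothing says which section governs.

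If going off study ends outcome collection before the one-month window closes, the participant remains in the intention-to-treat set by name but brings no outcome to the Pearson chi-square test. Sections 13 and 14 mention missing data only as a feasibility topic at the interim analysis and give no rule for a missing primary outcome.

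The reasons for removal may not be neutral. The listed side effects of starch are mainly gastrointestinal, and the comparator is a different, digestible starch, so tolerability could differ by arm. People who are getting sicker may also find it harder to comply. Losing their later admissions unevenly would bias the primary comparison. Outcomes not collected at the time may not be recoverable at analysis.

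**Working it through.** **1. The sections side by side.**

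| Reason for leaving | Within the Off Treatment exception? | Listed under Off Study? | Follow-up expressly ended? |
|---|---|---|---|
| Consent withdrawn for all procedures | Yes | Yes | Yes |
| Loss of ability to consent freely | Yes (no limit stated) | Yes (incarceration) | No |
| Unable to comply | No | Yes | No |
| Investigator best-interest judgement | No | Yes | No |
| Safety, behavioral, administrative | No | Yes | No |

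The last three rows are the conflict. That they end follow-up is an inference from the separate headings and from the rest of the off-study list, which includes study termination and completion of follow-up.

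**2. The plan's sample size.** Inputs from Section 14: 14% vs 9%, two-sided alpha 0.04, 80% power. Allocation of 1:1 is assumed, because no ratio is stated.

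n per arm = [z(α/2)·√(2·p̄(1−p̄)) + z(β)·√(p1(1−p1) + p2(1−p2))]² / (p1−p2)²

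With p̄ = 0.115: [2.0537·√0.20355 + 0.8416·√0.2023]² / 0.0025 = 681.3, so 682 per arm and 1364 in total. The stated 1362 is reproduced to within rounding. Enrolling 1500 leaves room for 1500 − 1362 = 138 participants (9.2%) without an outcome.

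**3. Size of the possible bias.** Take no true effect and 14% admission in both arms. Let m be the share of an arm removed and r the admission risk among those removed. If all their later admissions are lost, the rate in the retained group is

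retained = (0.14 − m·r) / (1 − m)

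The values of m and r are assumptions. The documents give neither. For example, with m = 8% and r = 28%: (0.14 − 0.0224)/0.92 = 12.78%.

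| Removed, RPS vs placebo | r | Retained, RPS | Retained, placebo | Spurious benefit | Complete-case type I error at 0.05 |
|---|---|---|---|---|---|
| 8% vs 3% | 28% | 12.78% | 13.57% | 0.8 points | about 7% |
| 8% vs 3% | 42% | 11.57% | 13.13% | 1.6 points | about 15% |
| 10% vs 2% | 28% | 12.44% | 13.71% | 1.3 points | about 11% |
| 10% vs 2% | 42% | 10.89% | 13.43% | 2.5 points | about 31% |

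The type I error column takes 750 randomized per arm and a normal approximation to the chi-square test.

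**4. Null cases.** If r = 14%, the formula returns 14% in both arms whatever the removal shares. If m and r are the same in both arms, both retained rates fall equally and the difference is zero. Bias therefore needs removal that differs by arm and is also prognostic.

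**5. Relation to the loss allowance.** Overall removal in these scenarios is (8% + 3%)/2 = 5.5% or (10% + 2%)/2 = 6%. Both lie inside the 10% that the plan allows for. The allowance protects power but not against this bias.

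**The case against.** Much of the protocol already favours retention. Product held for more than three days leads to removal from treatment with the participant kept under intention to treat. Voluntary withdrawal from treatment is an off-treatment reason in its own right under Duration of Therapy. Participants removed for persistent adverse events thought due to treatment are followed to resolution or stabilization. Those who go off study are not replaced. All of this stands. It narrows the conflict to inability to comply and the investigator-discretion reasons, but does not settle it.

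A reader might infer more than the documents support in four places:

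- **That every off-study item ends follow-up by rule.** Only the consent item says so. For the others it is a reasonable inference.
- **That loss to follow-up breaches the stated exception.** It is an event rather than an exemption. Its wording is permissive, it refers to being unable to locate the subject to document hospitalization, and contact attempts over four months must be documented. What remains is that failed phone contact alone should not end ascertainment while EHR review is scheduled.
- **That the free-consent wording exempts a sedated, ventilated participant.** This is strained. Off Study Criteria explains the phrase as incarceration, and ventilation outcomes are planned as exploratory objectives. Only the mismatch in wording is real.
- **That treatment-related dropout is shown.** The side-effect percentages are for starch without separation by arm, most patients are said to have no symptoms, and both arms step up the dose. Differential, prognostic removal is plausible but not established.

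It is also fair to say that the EHR alone may not capture every event. Admissions outside the system can be missed, and the temperature and symptom outcomes are reported by the patient.

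**Conclusion.** The inconsistency is real and confined to two groups of off-study reasons: inability to comply, and investigator discretion or best-interest judgement. Neither is within the exception in Off Treatment Criteria. Read in the natural way, they can leave intention-to-treat participants without a primary outcome, and the plan has no rule for that case. This undermines the intention-to-treat analysis in practice but does not contradict it on paper, since the protocol keeps these people in the analysis set.

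The possible bias is 0.8 to 2.5 points against the 5-point target, wholly under assumed removal shares and risks, and it would favour whichever arm lost more high-risk participants. It is zero if removal is equal or removed participants are at average risk. The correction concerns the primary endpoint, is cheap, and needs to be in place while outcomes are being collected.

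**What to change.** 1. Reconcile Off Treatment Criteria and Off Study Criteria so that inability to comply, best-interest judgement, and safety, behavioral or administrative reasons may end product and, if needed, calls, but do not end outcome ascertainment. When product is stopped is a clinical matter that this change leaves alone.
2. Continue the scheduled EHR review through the primary window and to day 120 unless the participant withdraws permission for it or the incarceration case applies. Accept that withdrawal orally or in writing, since the Alternatives paragraph in Section VI allows participants to withdraw by telling staff.
3. Record the level of withdrawal: product only, product and calls, or everything including EHR.
4. Code lost to follow-up for the primary outcome only when EHR review of the full window cannot establish hospitalization status.
5. Align the wording on ability to consent freely in Off Treatment Criteria with the incarceration wording in Off Study Criteria.
6. State in Section 14 how any primary outcome still missing will be handled, with a sensitivity analysis.

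The cost is protocol and consent wording, a short withdrawal form and a few more EHR checks. EHR review may still miss outside admissions and cannot supply the patient-reported secondary outcomes.

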### **Subject Replacement**

If subject needs to go off study after randomization, protocol dictates that subject cannot be replaced given the intention to treat nature of the protocol.

### **Screening baseline procedures**

Assessments performed exclusively to determine eligibility for this study will be done only after obtaining informed consent. Assessments performed for clinical indications (not exclusively to determine study eligibility) such as COVID testing may be used for baseline values even if the studies were done before informed consent was obtained.

All screening procedures must be performed within 7 days prior to registration unless otherwise stated. The screening procedures include:

- 1 Informed Consent
- 2 Medical history: Complete medical and surgical history
- 3 Demographics: Age, gender, race, ethnicity
- 4 Review subject eligibility criteria
- 5 Review previous and concomitant medications
- 6 Adverse event assessment

### **Procedures during treatment and follow up procedures**

*Assessment for primary objective of hospitalization at one month via phone and EHR:*

Every 2 days phone questionnaires (**see attached questionnaire**) and EHR review for the first 14 days followed by once weekly phone call and EHR review to complete a month follow up from last dose of treatment.

*Assessment for secondary objectives of TTCA and symptom severity score via phone and EHR:*

Every 2 day phone questionnaires (**see attached questionnaire**) and EHR review for the first 14 days followed by once weekly phone call and EHR review to complete a month follow up from last dose of treatment.

*Assessment of exploratory objectives*

EHR review to complete 4 months follow up from COVID positive test

### **Safety and Tolerability**

Analyses will be performed for all subjects having received at least one dose of study drug.

*Assessment of adverse events (**outlined in Table 3 above**)*

Every 2-day phone questionnaires (**Table 4**) and EHR review for the first 14 days followed by once weekly to complete a month follow up from last dose of treatment. Subjects will be followed for adverse events for at least 30 days after the last dose of study treatment. Subjects removed from treatment for persistent adverse events thought to be due to interventional treatment will be followed until resolution or stabilization of the adverse event.

**Table 4:** Time and Events

|                                   | Pre-Study  | Treatment Period/
Phone follow-up
(14 days) |                          | Follow-Up Period with phone and
electronic medical record (EHR) review |                         |                       |                       |
|-----------------------------------|------------|---|--------------------------|---|-------------------------|-----------------------|-----------------------|
| Observations                      | Enrollment | Day 1-14  | Every 2 days
day 0-14 | Every 7 days
through Day
30 from last
dose of
treatment       | Day 60
+/- 7
days | Day +90
+/- 7 days | Day 120
+/- 7 days |
| Informed
Consent
(phone)    | X          |   |                          |   |                         |                       |                       |
| Assessment of
co-morbidities   | X          |   |                          |   |                         |                       |                       |
| Study Agent                       |            | X   | X                        |   |                         |                       |                       |
| Side Effects                      | X          |   | X                        | X   |                         |                       |                       |
| Phone
Symptom
Questionnaire |            |   | X                        | X   |                         |                       |                       |
| Assessment of
medication use   | X          |   | X                        |   |                         |                       |                       |
| Assessment of
Hospitalization  |            |   | X                        | X   |                         |                       |                       |
| EHR review                        | X          | X   | X                        | X   | X                       | X                     | X                     |

**Section 5. Subject Population:** Provide a detailed description of the types of human subjects who will be recruited into this study.

Participants >18 years of age with COVID-19 positive status and who are English speaking and do not require hospitalization. Upon enrollment participants cannot be hospitalized and cannot be actively enrolled in any other interventional trials. Participants with any allergy to potato or corn starch or inability or difficulty swallowing solids/liquids will also be excluded. For full inclusion and exclusion criteria, please refer to **Table 1** above.

**Section 6. Subject classification:** Check off all classifications of subjects that will be specifically recruited for enrollment in the research project. Will subjects who may require additional safeguards or other considerations be enrolled in the study? If so, identify the population of subjects requiring special safeguards and provide a justification for their involvement. N/A

NOTE: Is this research proposal designed to enroll children who are wards of the state as potential subjects?

Yes  No

**Section 7. Inclusion/Exclusion Criteria:** What are the criteria used to determine subject inclusion or exclusion?

Assessments performed exclusively to determine eligibility for this study will be done only after obtaining informed consent. Assessments performed for clinical indications (not exclusively to determine study eligibility) such as COVID testing may be used for baseline values even if the studies were done before informed consent was obtained.

All screening procedures must be performed within 7 days prior to registration unless otherwise stated. The screening procedures include:

- 1 Informed Consent
- 2 Medical history: Complete medical and surgical history
- 3 Demographics: Age, gender, race, ethnicity
- 4 Review subject eligibility criteria
- 5 Review previous and concomitant medications
- 6 Adverse event assessment

